2. INTRODUCTION: BACKGROUND INFORMATION AND CLINICAL SIGNIFICANCE

2.1 Background information and clinical significance

Rapid sequence intubation (RSI) is the most common method of intubation used in the ED.¹ RSI involves the immediate administration of a paralytic agent following delivery of an induction agent that brings about unresponsiveness; a procedure which aims for successful endotracheal intubation with no ventilation via bag-valve-mask while awaiting the onset of paralysis. Under these circumstances, the maintenance of oxygen saturation during the apnoeic phase depends on the patient's underlying oxygen reserve, the adequacy of pre-oxygenation and the ability to insufflate the apnoeic lungs with oxygen (apnoeic oxygenation).

Critically ill patients have shorter safe apnoeic time (defined as duration of apnoea where SpO_2 remains $\geq 90\%$)² due to physiological stressors that accompany critical illnesses, such as decreased cardiac output, increased shunting and reduced pulmonary reserves. Once the SpO_2 reading approaches 90%, it can rapidly drop to $< 70\%$ (a critical hypoxic state) within seconds³ for two reasons. Firstly, a SpO_2 of 90% represents the steep gradient of the oxygen dissociation curve (Figure 1), where a small change in the arterial partial pressure of oxygen (PaO_2) results in a large change in haemoglobin oxygen binding capacity.⁴ Secondly, the pulse oximeter devices routinely used to measure SpO_2 have damped circuitry to prevent fluctuating readings. However, this property may delay recognition of falling haemoglobin oxygen saturation⁵ and up to 47% of patients may experience latency in SpO_2 readings of up to 2 minutes.⁶ Furthermore, with increasing prevalence of obesity in Singapore⁷ from increasing affluence, a large proportion of our critically ill patients are also obese, and obesity can further shorten safe apnoeic times. Benumof et al. estimated that a moderately ill normal-sized adult would reach an SpO_2 of 90% at slightly under 5 minutes, while a 127kg obese adult would reach such a level within 2.5 to 3 minutes⁸ (Figure 2).

[figure not shown]

Figure 1. Oxyhaemoglobin dissociation curve of a healthy individual⁴

[figure not shown]

Figure 2. Arterial oxyhaemoglobin saturation (SaO_2) versus time of apnoea in an obese adult, a 10kg, and in a moderately ill adult, compared with a healthy adult. $F_{\text{A}}\text{O}_2$, Fractional alveolar oxygen concentration; VE , expired volume⁷

Profound hypoxaemia during intubation results in higher proportions of peri-intubation cardiac arrest, brain injury and death.^{3,9} The risk of adverse outcomes escalates with increasing number of attempts at endotracheal intubation and with development of hypoxia.¹⁰⁻¹² Prolongation of safe apnoea time would ameliorate some of these negative outcomes, by preventing hypoxia and allowing more time to achieve successful intubation without resorting to bag-mask ventilation to re-oxygenate the patient.

Adequate pre-oxygenation is the cornerstone of successful RSI and an essential step to achieving prolonged safe apnoeic times during intubation.² Pre-oxygenation with high fraction of inspired oxygen (FiO_2) de-nitrogenates the lungs, maximises oxygen reserve and oxygen saturation in the bloodstream.³ The standard of care is to apply a non-rebreather mask (NRM) with tidal volume breathing for 3 minutes for pre-oxygenation. However, depending on the patients respiratory rate and depth of breathing (i.e. their minute volume) the actual FiO_2 delivered varies from 0.8 to 0.6,¹³ sometimes even lower. Other more efficacious methods such as applying positive airway pressure and pre-oxygenating in a head-up position of 20 degrees have been described, but are not always possible in emergency situations or with obtunded patients.^{14,15}

High flow nasal cannula (HFNC) oxygenation has been gaining interest as an alternative method of pre-oxygenation and apnoeic oxygenation.¹⁶ It can deliver up to 60L/min of oxygen and FiO_2 of 1.0. As it is

humidified and heated, the high flow is well tolerated by awake patients.¹⁷ Moreover, the high flow has been shown to wash out carbon dioxide in anatomical dead space, create positive airway pressure adequate enough for alveolar recruitment and maintain a constant FiO₂, regardless of the patient's minute volume.¹⁶ Additionally, it has the convenience of continuing oxygenation during the apnoeic phase after induction and paralysis, since the high flow maintains a positive end expiratory pressure and can insufflate the lungs, resulting in apnoeic oxygenation. Apnoeic oxygenation is possible due to differential solubility of oxygen and carbon dioxide in blood. Carbon dioxide is more soluble and therefore moves less readily down its concentration gradient from the bloodstream into the alveoli during apnoea. As a result, more oxygen moves from the alveoli into the bloodstream. This creates a sub-atmospheric pressure in the alveoli, allowing oxygen to flow from the pharynx to the alveoli during apnoea. Despite this sensible physiological rationale, a recent large randomised controlled trial reported no difference in median lowest arterial oxygen saturation in ICU patients with apnoeic oxygenation using 15L/min of nasal cannula compared with no apnoeic oxygenation at all.¹⁸ However, limitations in this study prevent definitive conclusions to be drawn. Firstly, the oxygen flow of 15L/min was delivered through routine nasal cannulae, which are not designed for such flows. Secondly, a flow rate of 15L/min may not be high enough to provide apnoeic oxygenation. It has been shown that flows of 30L/min are necessary to generate positive airway pressures.¹⁹ Thirdly, the cohort in the study consisted of mostly medical ICU patients with advanced respiratory failure, where 15L/min of oxygenation may not generate enough positive airway pressure to overcome pulmonary shunting. Furthermore, the results cannot be generalised to patients who do not typically present to medical ICUs, for instance patients with severe trauma or a surgical diagnosis.

There have been conflicting results from previous studies evaluating pre-oxygenation and apnoeic oxygenation using true HFNC. The PREOXYFLOW trial is the largest randomised controlled trial (RCT) to date (n=124) and found no difference in the lowest SpO₂ achieved when HFNC oxygenation was compared to high fraction-inspired oxygen facial mask for pre-oxygenation.²⁰ These results differ from another quasi-experimental before-after study (n=101), which showed that patients who were pre-oxygenated with HFNC had significantly higher SpO₂ during the apnoeic phase.²¹ Both studies were conducted in ICU patients and continued the HFNC during the apnoeic phase for apnoeic oxygenation. In addition to the contradictory findings by the 2 studies, it is also difficult to conclude whether the favourable results were attributable to the effect of HFNC during pre-oxygenation or apnoeic oxygenation.

Until now, there have been no studies conducted in the ED investigating the use of HFNC for pre- and apnoeic oxygenation. The incidence of failed intubations in the emergency setting is estimated to be 20 times that compared to intubation done electively²² and ED patients differ from ICU patients because they are less likely to have been fasted, increasing the risk of aspiration if re-oxygenation with bag valve mask is required during the intubation attempts. Aspiration of gastric contents contributes to increased risk of death during intubation.²³ Furthermore, hypoxia from failure to intubate is associated with increased ICU length of stay, irreversible brain damage, increased number of ventilated days and higher incidence of tracheostomy.²⁴ This translates to longer hospital stays, adversely affecting overall bed occupancy, as well as higher healthcare costs. Given the existing high occupancy in Singapore's restructured hospitals, which is expected to worsen as the population ages, it is vital that we prevent such adverse events from occurring by prolonging safe apnoea times for intubation (i.e. maintain lowest SpO₂ above 90%), without the need for bag-valve-mask ventilation for re-oxygenation during RSI. If our hypothesis is confirmed, the results from this study could potentially change current clinical practice and reduce demands on an already stressed healthcare system.

2.2 Potential benefits and risks

Potential benefits include a longer safe apnoeic time during rapid sequence intubation (i.e. SpO₂ maintains more than or equal to 90% after intubation til successful intubation). Although well tolerated by most patients, delivering HFNC oxygenation may have the following side effects or risks such as:

- Mild discomfort due to the high flow (approximately 12% risk),
- Dryness of the nose (level of dryness approximately 50% with high flow oxygenation compared with 95% in conventional oxygen therapy), and
- Low oxygen saturation during the intubation process (less than 5% risk): this will be similar for control and intervention groups.

Continuous SpO₂ monitoring will be performed to ensure that SpO₂ is maintained above 95% for pre-oxygenation. Previous studies using nasal oxygenation for pre-oxygenation prior to intubation were also able to maintain saturations at 100%,²¹ and showed no difference in SpO₂ at end of pre-oxygenation between the use of high flow face mask or nasal cannula.²⁰

3. **SPECIFIC AIMS & HYPOTHESIS**

The purpose of this clinical trial is to determine the best practices for maintaining oxygenation during rapid sequence intubation of critically ill patients in the emergency department (ED). Therefore, this multicentre randomised clinical trial is designed to test the hypothesis that the use of humidified high flow oxygenation via nasal cannula at 60L/min for **pre-oxygenation** and **apnoeic oxygenation** maintains higher oxygen saturation (SpO₂) compared with current usual care of non-rebreather mask for pre-oxygenation and standard nasal cannula of 15L/min for apnoeic oxygenation.

We expect to confirm our hypotheses by demonstrating that the use of humidified high flow oxygenation at 60L/min via nasal cannula (HFNC) during pre-oxygenation, as well as for apnoeic oxygenation, would improve the lowest recorded SpO₂ during intubation, and consequently increase the safe apnoeic time during rapid sequence intubation in the ED.

4. **STUDY DESIGN**

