4.1 Description of study design

Overview

[figure not shown]

Figure 3.
Randomisation flow chart.

*Usual care for pre-oxygenation involves the use of non-rebreather mask

Target population and study site

This will be a randomised controlled study (Figure 3), enrolling adult patients aged 21 years and above, who require RSI due to medical, surgical and traumatic conditions, in the Emergency Departments of National University Hospital and Ng Teng Fong General Hospital, Singapore.

Randomisation

Subjects will be randomised at equal ratio into 2 treatment combinations (Figure 3). Random blocks of variable sizes will be selected via a web-based randomisation service. The block lengths will be kept unknown to the site as per ICH E9 guideline. However, block randomisation will ensure the numbers in each group will remain similar throughout the study, should we fail to recruit the targeted number of patients.

Allocation concealment will be maintained until registration and randomisation process is completed. However, due to the nature of the intervention, it will not be possible to blind the treating clinician, ED staff members or patient after allocation has occurred. A possible concern is whether the results will be biased due to lack of blinding. As the outcome measures in our study are objective physiological measurements, the risk of bias remains low.²⁷ Clinicians in the admitting ICU will be blinded to the patients' allocation to any of the study arms.

Treatment protocol

In the intervention arm, the patients will receive oxygenation with 60L/min using the AIRVO™ 2 Humidifier with Integrated Flow Generator (Fisher & Paykel Healthcare, Auckland, New Zealand) during the pre- and apnoeic oxygenation phases.

The control group will be managed in accordance with current best practice by performing pre-oxygenation using NRM that has a FiO₂ of 0.6 to 0.8¹³ and given 15L/min of oxygen via nasal cannula (non-humidified, from wall supply).

Both groups will receive 3 minutes of pre-oxygenation.^{3,28,29} Premedication (if required) will be given 3 minutes prior to RSI, i.e. at the start of pre-oxygenation.³⁰ The lowest SpO₂ achieved from time of administration of paralytic agent until quantitative end-tidal CO₂ (ETCO₂) is detected for the first intubation attempt will be measured for all groups, together with the variables listed below.

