8. STATISTICAL CONSIDERATION

8.1 Sample size calculation

Based on our preliminary data and previous studies, we anticipate a standard deviation of 14% in lowest SpO₂. Enrolment of **184 patients** (92 patients in each of control and intervention groups) will provide statistical power of 80% (with a two-sided α of 0.05) to detect a 6% difference in lowest SpO₂, allowing for a 5% dropout.

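### Does the under-5% risk of low saturation in Section 2.2 undermine the SD of 14 and the 6-point difference behind the sample size?

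*Protocol*

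**What the plan says.** Section 2.2 names longer maintenance of SpO₂ at or above 90% as the potential benefit. It then lists three possible side effects or risks of delivering high-flow nasal oxygen. The third is "Low oxygen saturation during the intubation process (less than 5% risk): this will be similar for control and intervention groups". The sentence gives no saturation threshold and no source.

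Section 3 expects that high-flow oxygen "would improve the lowest recorded SpO₂ during intubation". Section 4.2 makes lowest SpO₂ during the first attempt the primary endpoint and incidence of SpO₂ below 90% one of the secondary endpoints.

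Section 8.1, citing preliminary data and previous studies, states "we anticipate a standard deviation of 14% in lowest SpO₂". It says that 184 patients, 92 per arm, "will provide statistical power of 80% (with a two-sided α of 0.05") "to detect a 6% difference in lowest SpO₂, allowing for a 5% dropout". No mean lowest SpO₂ is given for either arm.

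**The concern.** Two things look wrong at first sight.

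- **The size of the risk.** A variable that cannot exceed 100% can have an SD of 14 only if a sizeable share of values lies far below the ceiling. A risk under 5% suggests that almost nobody does. If low means below 90%, the threshold used a few lines earlier and in Section 4.2, the two sections seem to describe different populations.
- **The word similar.** The trial is run because high-flow oxygen is expected to raise the lowest SpO₂, yet the risk sentence expects no difference between arms.

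If both readings were right, one of two consequences would follow. Either the desaturation risk is understated several-fold in the risk-benefit section, or the SD and the 6-point target rest on a false premise and the stated 80% power cannot be relied on.

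**Working it through.** **1. Reproduce the sample size.** Inputs from Section 8.1: difference 6, SD 14, two-sided α 0.05, power 80%, dropout 5%. Allocation is equal (Section 4.1: "Subjects will be randomised at equal ratio into 2 treatment combinations").

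- Normal approximation: n per arm = 2 × [14 × (1.960 + 0.842) / 6]² = 85.5, so 86.
- t-based: 86.4, so 87 per arm. Then 87 / 0.95 = 91.6, so 92 per arm and 184 in total, which is the protocol's figure.
- Power with 87 evaluable per arm is 80.3% (t-based).

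The under-5% figure enters nowhere. The only 5% in the calculation besides α is the dropout allowance.

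**2. Largest SD if at most 5% of patients are below 90%.** Put 5% at a floor L and the rest at 90 or 100. The variance is greatest when the mean is 95, which gives SD² = 0.05 × (95 − L)² + 0.95 × 5².

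| Floor L | SD² | Largest SD |
|---|---|---|
| 70 | 31.25 + 23.75 = 55 | 7.4 |
| 60 | 61.25 + 23.75 = 85 | 9.2 |
| 50 | 101.25 + 23.75 = 125 | 11.2 |
| 40 | 151.25 + 23.75 = 175 | 13.2 |
| 36 | 174.05 + 23.75 = 197.8 | 14.06 |

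An SD of 14 is therefore reachable, but only if nearly all of the 5% sit at about 36% saturation. With a floor of 30%, all the figures can be met together: at most 5% below 90% in both arms, a 6-point difference, and a pooled SD of up to 15.0. That is implausible but not impossible.

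**3. Share of control patients below a threshold if the SD is 14.** The control mean is an assumption, taken from 85 to 94, since 94 is the highest that leaves room for +6. The shapes are a beta distribution and a normal censored at 100.

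| Threshold | Implied share of control arm |
|---|---|
| below 90% | 16% to 56% |
| below 80% | 10% to 34% |
| below 70% | 7% to 16% |
| below 60% | 4.5% to 6.9% |
| below 50% | 1.6% to 3.0% |

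The conflict is large at 90%, modest at 70% (the level Section 2.1 calls critical hypoxia), marginal at 60% and absent at 50%.

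**4. What if the under-5% figure is right, at the 90% threshold?** The SD would then be smaller than 14. With an SD of 11.2 (floor 50%), a 6-point difference needs 55 per arm; with 7.4 (floor 70%), 24 per arm. Against 87 evaluable per arm, the trial would be over-powered for 6 points.

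**5. Does similar contradict the hypothesis?** Take 5% at 75 in both arms, with the rest at 91.5 in control and 98 in the intervention arm.

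- Control mean: 0.05 × 75 + 0.95 × 91.5 = 90.7.
- Intervention mean: 0.05 × 75 + 0.95 × 98 = 96.9.

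The gain is 6.2 points with the same incidence below 90%. The SDs here are far below 14, so this is an illustration only. It shows that a difference in mean lowest SpO₂ and an equal proportion below a threshold are not logically opposed.

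**The case for a change.** The strongest case for acting is that Section 2.2 itself defines the benefit by the 90% threshold, so a reader will naturally take low to mean below 90%. On that reading an under-5% risk is out of line with an SD of 14 by a factor of roughly 3 to 11 (16/5 to 56/5), and even at 70% the implied control share stays above 5%. The word similar sits next to a hypothesis of benefit and a between-arm comparison of SpO₂ below 90%. If the under-5% figure were true, most control patients could be near the ceiling. For example, with 5% at 75 and the rest at 98 the mean is 96.9, which leaves little more than 3 points to gain, so extra precision for 6 points would be of little use.

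Part of this stands. The sentence is undefined and unsourced, and under ordinary distributions it does not match Section 8.1 at 90%, 80% or 70%. The rest does not carry to the plan:

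- The 3-point ceiling comes from placing 95% of control patients at 98, which is a choice made for the example; step 5 shows another choice that leaves room for 6.
- Of the two figures, the SD has a stated basis and the under-5% has none, so the mismatch casts doubt on the risk sentence rather than on the sample size.
- In a list of possible harms of the device, similar can fairly be read as saying that no added desaturation is expected from high-flow oxygen. It is not a design assumption.

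**Conclusion.** The concern does not hold as a point against the plan. Section 2.2 contains a loose sentence that fits badly with an SD of 14 if low means below 90%: about 16% to 56% of control patients would be below that level, on assumed control means of 85 to 94 and the two shapes used. The mismatch shrinks as the unstated threshold falls and is gone at 50%. Nor is it a mathematical contradiction.

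The sample size of 184 reproduces from Section 8.1 alone. The primary endpoint, the secondary endpoints and the intention-to-treat comparison in Section 8.2 make no use of the under-5% figure, and the trial will observe the incidence of SpO₂ below 90% in each arm whatever Section 2.2 expected. Analysts following the protocol as written would run the same test, report the same interval and reach the same conclusion. What remains is clerical: an undefined term without a source in a risk paragraph. It has no consequence for design, power or analysis.

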4.1 Description of study design

Overview

[figure not shown]

Figure 3.
Randomisation flow chart.

*Usual care for pre-oxygenation involves the use of non-rebreather mask

Target population and study site

This will be a randomised controlled study (Figure 3), enrolling adult patients aged 21 years and above, who require RSI due to medical, surgical and traumatic conditions, in the Emergency Departments of National University Hospital and Ng Teng Fong General Hospital, Singapore.

Randomisation

Subjects will be randomised at equal ratio into 2 treatment combinations (Figure 3). Random blocks of variable sizes will be selected via a web-based randomisation service. The block lengths will be kept unknown to the site as per ICH E9 guideline. However, block randomisation will ensure the numbers in each group will remain similar throughout the study, should we fail to recruit the targeted number of patients.

Allocation concealment will be maintained until registration and randomisation process is completed. However, due to the nature of the intervention, it will not be possible to blind the treating clinician, ED staff members or patient after allocation has occurred. A possible concern is whether the results will be biased due to lack of blinding. As the outcome measures in our study are objective physiological measurements, the risk of bias remains low.²⁷ Clinicians in the admitting ICU will be blinded to the patients' allocation to any of the study arms.

Treatment protocol

In the intervention arm, the patients will receive oxygenation with 60L/min using the AIRVO™ 2 Humidifier with Integrated Flow Generator (Fisher & Paykel Healthcare, Auckland, New Zealand) during the pre- and apnoeic oxygenation phases.

The control group will be managed in accordance with current best practice by performing pre-oxygenation using NRM that has a FiO₂ of 0.6 to 0.8¹³ and given 15L/min of oxygen via nasal cannula (non-humidified, from wall supply).

Both groups will receive 3 minutes of pre-oxygenation.^{3,28,29} Premedication (if required) will be given 3 minutes prior to RSI, i.e. at the start of pre-oxygenation.³⁰ The lowest SpO₂ achieved from time of administration of paralytic agent until quantitative end-tidal CO₂ (ETCO₂) is detected for the first intubation attempt will be measured for all groups, together with the variables listed below.

4.2 Study endpoints

1. Primary endpoint

- Lowest SpO₂ achieved during first intubation attempt
 - From time of administration of paralytic agent until quantitative ETCO₂ is detected post-intubation
 - First intubation attempt is defined as first attempt to insert endotracheal tube into oropharynx

SpO₂ will be measured using the pulse oximeter of Philips Intellivue MP30 Patient Monitor.

2. Secondary endpoints

- Number of attempts at intubation
- Safe apnoea time during intubation
- Incidence of SpO₂ < 90%
- Peri-intubation adverse events (see below under Study Procedures)
- Length of time to successful intubation
- Incidence of ventilator associated pneumonia and aspiration pneumonia
- Number of ventilated days
- In-hospital mortality in ICU and on discharge
- Highest Sequential Organ Failure Assessment (SOFA) score
- Incidence of acute respiratory distress syndrome (ARDS)
- Lowest PaO₂ : FiO₂ ratio while intubated

5. STUDY ENROLMENT AND WITHDRAWAL

5.1 Inclusion criteria

Adult patients aged 21 years and above, who require RSI due to medical, surgical and traumatic conditions, in the Emergency Departments of National University Hospital will be eligible for study enrolment.

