8.2 General approach for statistical analysis

The primary analysis will be an intention-to-treat analysis, comparing the primary outcome of lowest SpO₂ achieved between two groups. Descriptive statistics of lowest SpO₂ (e.g. mean, standard deviation, median and interquartile range) will be reported for each group. Comparison of mean (or median) lowest SpO₂ between groups will be made using two-sample *t*-test or non-parametric test as appropriate. 95% confidence intervals of difference in lowest SpO₂ will be provided. Categorical data will be compared using the Fisher's exact test. We will use linear and logistic regression to adjust our findings if there are important differences between the study arms that might confound the results.

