9. DATA HANDLING AND RECORD KEEPING

The Research Electronic Data Capture (REDCap) system will be used and maintained at SCRI's secure server. Authorised personnel will be assigned user IDs and passwords to gain access to the database. Entered data will be systematically checked by built-in edit checks.

The study participant's information and research data will be securely stored at the dedicated research computers in the NUH and NTFGH Emergency Departments for internal use during the study. The research computers are password protected and located in the Emergency Department administrative offices which are only accessible to authorised personnel by card access. Individual participants and their research data will be identified by a unique study identification number. Patients' identifiers and research data will be stored separately.

10. **CONFLICT OF INTEREST**

The PI and co-investigators declare no conflict of interests.

11. **REFERENCES**

4. Weingart SD. Preoxygenation, reoxygenation, and delayed sequence intubation in the emergency department. *J Emerg Med.* 2011;40(6):661-667.

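### Does the one-hospital inclusion criterion in Section 5.1 undermine a trial that is otherwise described as two-hospital?

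*Protocol*

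**What the plan says.** Protocol Section 5.1 is one sentence and is the whole of the inclusion criteria. It sets the age limit and the need for rapid sequence intubation, then places eligible patients "in the Emergency Departments of National University Hospital will be eligible for study enrolment". No second hospital appears.

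Section 4.1, under its sub-heading on target population and study site, describes the same patients in almost the same sentence but enrols them "in the Emergency Departments of National University Hospital and Ng Teng Fong General Hospital, Singapore".

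Two other places bear on the number of sites. Section 3 says that "this multicentre randomised clinical trial is designed to test the hypothesis", without naming or counting the sites. Section 9 places participant information on "dedicated research computers in the NUH and NTFGH Emergency Departments for internal use during the study".

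On analysis, Section 8.2 says: "The primary analysis will be an intention-to-treat analysis". It compares lowest SpO₂ by a two-sample t-test or a non-parametric test, with regression adjustment if the arms differ in important ways. Section 4.1 describes blocked web-based randomisation with variable block sizes and mentions no stratification factor.

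**The concern.** Inclusion criteria are what investigators, monitors and ethics committees usually treat as the test of who may enter a trial. Here there is only one, and as worded it admits patients from one hospital. A strict reader would conclude that everyone enrolled at the second hospital was ineligible, in conflict with the study-site paragraph. If that reading were acted on, a whole site's patients could be logged as eligibility deviations or, at worst, challenged at analysis.

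A second thought follows from the first. If there are two hospitals, one might expect hospital to appear in the randomisation or in the primary comparison, and the protocol mentions it in neither.

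**Working it through.** **1. The passages side by side**

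| Place in protocol | What it says about sites | What it establishes |
|---|---|---|
| Section 5.1 | National University Hospital only, after a plural for its departments | Eligibility, one hospital |
| Section 4.1 | National University Hospital and Ng Teng Fong General Hospital | Enrolment at two hospitals |
| Section 3 | Multicentre | More than one site, unnamed |
| Section 9 | Data held at both emergency departments | Both sites take part; silent on enrolment |

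Only Section 4.1 states outright that patients are enrolled at the second hospital. Sections 3 and 9 corroborate it but are not separate enrolment rules. Nothing in the protocol gives a reason for restricting eligibility to one hospital. The near-identical sentence, and the plural left in front of a single hospital, point to an omitted name.

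**2. Does the sample size depend on it?**

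Inputs from Section 8.1: standard deviation 14, difference 6, two-sided α 0.05, power 80%, dropout 5%, 92 per arm.

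- Normal approximation: n = 2 × (1.96 + 0.842)² × 14² / 6² = 85.5, so 86 per arm. Then 86 / 0.95 = 90.5, so 91 per arm (182 in total).
- Two-sample t-test: n = 86.4, so 87 per arm. Then 87 / 0.95 = 91.6, so 92 per arm (184 in total), which is the protocol's figure.
- Power by t-test: 80.3% with 87 evaluable per arm, 82.4% with all 92.

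No input refers to the number of hospitals, so naming the second one changes none of these results.

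**3. Does the analysis set depend on it?**

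The primary analysis is by intention to treat, and the protocol sets no rule that removes randomised patients for failing an entry criterion. Patients from the second hospital are therefore analysed as randomised on either reading of Section 5.1. The comparison between arms is unchanged, and randomisation protects it in the same way.

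**4. Would a hospital term or stratum matter?**

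The protocol gives no site split and no expected difference between hospitals. The ranges here are assumptions: smaller hospital m = 40 to 80 of 184 patients, and hospitals differing by d = 2 to 8 points in mean lowest SpO₂.

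- Unadjusted standard error with 92 per arm: 14 × √(2/92) = 2.06 points (with 87 per arm, 14 × √(2/87) = 2.12).
- Between-hospital variance, with p = m/184: p(1 − p)d². Lowest: 0.217 × 0.783 × 4 = 0.68, which is 0.35% of 14² = 196. Highest: 0.435 × 0.565 × 64 = 15.73, which is 8.0% of 196.
- Adjusted standard error: 2.06 × √(1 − 0.0035) = 2.06, down to 2.06 × √(1 − 0.080) = 1.98.
- Chance shift in the treatment difference from site imbalance with no stratification: ±1.96 × d × 2 × SD(X) / 92, where X is the number of smaller-hospital patients in one arm and SD(X) = √[(m/4) × (184 − m)/183]. For m = 40, d = 2, SD(X) = 2.81 and the 95% range is ±0.24 points. For m = 80, d = 8, SD(X) = 3.37 and it is ±1.15 points.

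That shift is random, not systematic. It is part of ordinary sampling error and does not bias the comparison. Even at the extreme, the gain in precision is 0.08 points on a standard error of about 2.

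**The case for a change.** The best case for acting is that Section 5.1 is the only inclusion criterion, an entire site falls outside its wording, and the repair is one line with no added patients. A statistical analysis plan would not be expected to mend an eligibility rule, so the error cannot be left to a later document. All of that is fair as a description, and the two sections ought to name the same hospitals.

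What does not stand is the claimed consequence. The protocol contains no rule on deviations that would turn second-hospital patients into recorded breaches, and it does not rank Section 5.1 above Section 4.1. A monitor who meets the discrepancy finds the answer in the study-site paragraph of the same document. The passages are therefore easy to reconcile, and the harm is an untidy record, not a doubtful result.

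The case for adding hospital to the randomisation or model is weaker still. It does not follow from a missing name in Section 5.1. Silence on strata is no evidence that there are none, because separate site lists may be set in the randomisation specification or the analysis plan, which are not at hand. Section 8.2 already allows regression adjustment if the arms differ in important ways. A mandatory hospital term would replace the stated t-test or non-parametric test with a model. Doing that after enrolment had begun, in a trial whose treating staff are not blinded, would carry a risk of its own for a small gain.

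**Conclusion.** Section 5.1 omits a hospital that Section 4.1 names, and Sections 3 and 9 are consistent with two sites. This is a clerical slip whose intended reading is plain from the protocol itself. Its effect on sample size, power, bias and the primary result is nil: 184 patients and 80.3% power with 87 evaluable per arm stand on either reading, and the intention-to-treat comparison includes the same patients. The wording can be aligned whenever the protocol is next edited, but no change to design, conduct or analysis follows.

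The conclusion that hospital adjustment offers little rests on the assumed ranges (40 to 80 patients at the smaller hospital, differences of 2 to 8 points). A much larger difference between hospitals would raise the gain in precision but would still not make the unadjusted comparison biased.
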